9.2.1.1 Spontaneously Reported Adverse Events

Spontaneously reported AEs; either volunteered by the patient, prompted by non-directed questioning or reported by an investigator will be documented on the eCRF.

9.2.2 **12-Lead ECGs**

Standard resting 12-lead ECGs will be obtained after patient is resting in the supine position for 10 minutes at Screening, post-dose completion (end of infusion) on Day 1 and Day 4 daily at Day 2-6 while patient hospitalized, at Day 7 and Day 28. Additional ECGs may be obtained if clinically indicated.

Overall interpretation and machine read intervals (HR, PR, QRS, QT, and QTc) will be recorded on the ECG eCRF. Clinically significant ECG findings that emerge after treatment will be recorded on the AE eCRF.

9.2.3 Laboratory Tests

All routine laboratory analyses will be conducted by a local laboratory and have been listed below. Laboratory tests will be obtained as indicated on the Schedule of Events table. When completing the safety laboratory tests there may be instances where the windows for two time points overlap due to time of study drug dosing, only one lab sample should be collected if time points overlap (see Sections 7.2.2 and 7.2.6).

Female patients of childbearing potential will have a serum pregnancy test at Screening and Day 28.

| Chemistry: PPD/CCI | | | |
|----------------------|--------|--|--|
| | | | |
| | | | |
| | | | |
| | | | |
| Hematology: PPD/CCI | | | |
| Hemulology. | | | |
| | | | |
| | | | |
| | | | |
| | | | |
| Urinalysis: PPD/CCI | | | |
| | | | |
| | l | | |
| Coagulation: PPD/CCI | I | | |
| Cougulation. | ı | | |
| Urine Drug Screen: | PD/CCI | | |
| Orine Drug Screen: | | | |
| | | | |
| | | | |

Note: If HIV antibody screening returns a positive result, test will be confirmed by Western Blot.

9.2.4 Vital Signs

Systolic/diastolic blood pressure, heart rate, respiratory rate, and temperature will be measured at:

- a. Screening
- b. Day 1 and Day 4 pre-dose and post-dose completion (end of infusion), Day 2, Day 7, and Day 28 (or Early Termination)
- c. If patient is in hospital on Day 3, Day 5, Day 6

Vital signs will be measured prior any blood collection. Blood pressure and heart rate will be measured after the patient has been resting (supine or sitting) for at least 3 minutes. Measurements will be taken at the times specified in the Schedule of Events table and will be recorded on the appropriate source document and eCRF.

[figure not shown]
9.2.5 **Physical Examination**

A physical examination will be conducted at the Screening Visit, Day 1, Day 2, daily on Day 3-6 (if in hospital), Day 7 and Day 28 (or Early Termination). It will include general appearance, evaluation of head, eyes, ears, nose, throat, neurological exam, weight and specific attention to pulmonary abnormalities, worsening in liver function as noted by increasing jaundice, ascites, or hepatic encephalopathy and presence of infection.

Any changes from baseline outside the normal range that emerge after treatment will be recorded on the AE eCRF.

9.2.6 **Biomarkers**

9.3 Adverse Events

9.3.1 **Definitions**

Adverse Event

An adverse event (AE) is any untoward medical occurrence in a patient or clinical investigation patient administered a pharmaceutical product and which does not necessarily have to have a causal relationship with this treatment. An AE can therefore be any unfavorable and unintended sign or symptom, including clinically significant laboratory values and test results, concomitant illness, accident, or worsening of an existing medical condition.

The following should not be recorded as an AE if noted at screening:

- A pre-planned procedure for an illness included in the patient's medical history, unless the condition for which the procedure was planned has worsened since prior to dosing. Please observe that complications to pre-planned procedures should be recorded as AEs
- A pre-existing condition found as a result of screening procedures

Any worsening in severity or frequency of a baseline concomitant illness or any new illness diagnosed in the trial period must be regarded as an AE.

Serious Adverse Event

A serious adverse event (SAE) is any adverse event that, at any dose:

Results in death

Is life-threatening

Life-threatening refers to an event in which the patient is at risk of death at the time of the event. It does not include an event that, had it occurred in a more severe form, might have caused death

Requires inpatient hospitalization or prolongation of existing hospitalization – Inpatient hospitalization includes an overnight admission

Results in persistent or significant disability/incapacity

Disability is defined as a substantial disruption of a person's ability to conduct normal life functions

Results in the birth of a child with a congenital anomaly/birth defect

Important medical events that may not result in death, be life threatening, or require hospitalization may be considered an SAE (when based upon appropriate medical judgment). These events may jeopardize the patient and may require medical or surgical intervention to prevent one of the outcomes listed above.

Note: Hospitalizations that occurred prior to the signing of informed consent, and where the underlying condition of AH for which the hospitalization was planned has not worsened will not be considered SAEs.

Unexpected Serious Adverse Event

An unexpected serious adverse event (USAE) is any serious adverse event that is independent of the underlying liver disease causality and is not consistent with information in the current Investigator's Brochure, the protocol, and the consent document.

Adverse Reaction

An adverse reaction (AR) is any untoward and unintended response to a test drug that has been considered to have a causal relationship with the treatment.

Suspected Unexpected Serious Adverse Reaction

A suspected unexpected serious adverse reaction (SUSAR) is an adverse reaction that is serious and where the nature or severity of which is not consistent with information in the current Investigator's Brochure.

Abnormal Laboratory Value as an AE

An abnormal laboratory value (i.e. any clinical laboratory abnormality or change that suggests a disease and/or organ toxicity and is of a severity that requires active management [i.e. change of test drug dose, discontinuation of test drug, medical treatment, more frequent follow-up or diagnostic investigation]), will be regarded as an AE. If clinical sequelae have been associated with a laboratory abnormality the diagnosis or medical condition should be reported (e.g. renal failure, hematuria) to replace the laboratory abnormality (e.g. elevated creatinine, urine RBC increased).

9.3.1.1 Classifications

Severity

The Investigator will evaluate the severity of each adverse event using the following definitions:

Mild – An event that is easily tolerated by the patient, causing minimal discomfort and not interfering with everyday activities (CTCAE Grade 1).

Moderate – An event that is sufficiently discomforting to interfere with normal everyday activities (CTCAE Grade 2).

Severe – An event that prevents normal everyday activities (CTCAE Grade 3-5).

Adverse events should be assessed according to the National Cancer Institute Common Terminology Criteria for Adverse Events (CTCAE) Version 4.0.

In the event of the occurrence of a severe adverse event, the Investigator will be instructed to immediately inform the medical monitor.

An AE that has been assessed as severe should not be confused with an SAE. Severity is a category utilized for rating the intensity of an event; and both AEs and SAEs can be assessed as severe. An event should be described as 'serious' when it meets one of the pre-defined outcomes as described in Section 9.3.1.

Causality

The Investigator is obligated to assess the relationship between test drug and the occurrence of each AE/SAE. The Investigator will use clinical judgment to determine if there is a reasonable possibility that the pharmacological action of the test drug was responsible for the AE/SAE being reported. Alternative causes such as natural history of the underlying diseases, concomitant therapy, other risk factors, and the temporal relationship of the event to the test drug will be considered and investigated. The Investigator will also consult the Clinical Investigator's Brochure and/or Product Information, for marketed products, in the determination of his/her assessment.

After careful medical consideration, the Investigator will evaluate the relationship of each adverse event to test drug applying the following definitions:

Probably Related – Good reasons and sufficient documentation to assume a causal relationship

Possibly related – A causal relationship is conceivable

Unlikely related – The event is most likely related to etiology other than the test drug

Not Related – Good reasons and sufficient documentation to exclude a causal relationship.

There may be situations when an SAE has occurred and the Investigator has minimal information to include in the initial report. However, it is very important that the Investigator always make an assessment of causality for every event prior to transmission of the SAE Report Form to the Sponsor (or designee).

9.3.2 Adverse Event Reporting

All events that meet the definition of an AE that occur in the period from when the patient has signed the informed consent form (ICF) through trial completion (final visit), or early

termination, must be recorded on the adverse event eCRF. All SAEs will be recorded on the appropriate eCRF and on the Serious Adverse Event Report Form from the time written informed consent has been obtained through trial completion (final visit), or early termination.

At each contact between the investigative site and the patient (visit or phone), after the patient has had an opportunity to spontaneously mention any problems, the Investigator should inquire about the occurrence of AEs. The following are examples of open-ended questions that may be used to obtain this information:

"How are you feeling?"

"Have you had any medical problems since your last visit/assessment?"

"Have you taken any new medicines, other than those given to you in this study, since your last visit/assessment?"

All AEs and SAEs will be documented in source records at each assessment time or when otherwise volunteered by the patient and recorded on the appropriate eCRF. Information to be collected includes the nature, date and time of onset, severity, duration, relationship to test drug, and outcome of the event. Even if the Investigator assesses the AE as not reasonably attributable to the test drug, its occurrence must be recorded in the source documents and reported on the eCRF along with the assessment of association.

The Investigator will treat the patient as medically required, and this may extend beyond the duration of the trial. The Investigator will record treatment and medications required to treat AEs on the appropriate eCRF(s). All SAEs, and any possibly/probably related severe AEs will be followed until resolution (no further changes in the event are expected, i.e., the point at which a patient experiencing such an AE is appropriately treated and stabilized even though they may continue to experience lingering sequelae that may never resolve.

DURECT's designee will evaluate all AEs with respect to seriousness, causality and expectedness in accordance with Directive 2001/20/EC (3) and FDA Guidelines. The expectedness of an AE will be determined according to the current version of the Investigators Brochure.

9.3.3 Reporting of Serious Adverse Events

Regardless of causality, the investigator must complete and submit an SAE form to within 24 hrs of

knowledge of the event for all serious adverse events.

The Investigator must indicate the SAE's relationship to test drug and sign the SAE form. When additional relevant information (final diagnosis, outcome, results of specific investigations, etc.) becomes available, the investigator must record that follow-up information in the eCRF. Follow-up information should be recorded according to the process used for reporting the initial event as described above. The investigator will follow all reportable events (i.e., SAEs) until resolution. Resolution means no further changes in the event would be expected, i.e., the point at which a patient experiencing such an AE is appropriately treated and stabilized even though they may continue to experience lingering non-serious sequelae that may never resolve.

will follow all SAEs until resolution (no further changes in the event are expected, i.e., the point at which a patient experiencing such an AE is appropriately treated and stabilized even though they may continue to experience lingering sequelae that may never resolve).

PPD/CCI will report all SAEs to DURECT within 1 business day of receipt.

All serious adverse events will also be reported on the AE CRF and concomitant medications administered in association with the serious AE will be documented on the CM CRF.

If a serious adverse event occurs and comes to the attention of the Investigator after trial completion/termination within 30 days of test drug dosing or within 30 days of the last trial visit (whichever occurs later), it must be reported immediately to PPD/CCI in the same manner as the serious adverse events occurring during the trial. Investigators are not obligated to actively seek AEs from former study participants.

The Investigator must report SAEs to the IRB/IEC (per the IRB/IEC guidelines/SOPs), including all SAEs that have occurred at the investigative site and all trial related SAEs that have resulted in an expedited safety report to a regulatory agency. Concurrently, the Investigator must send DURECT documentation of such IRB/IEC notification or if reporting is not required immediately per IRB/IEC guidelines, then a copy of the local SOP stating the reporting guidelines should be supplied by the site to DURECT and the CRO.

DURECT complies with applicable regulatory requirement(s) related to the reporting of SUSARs to the competent authorities and the IRBs/IECs. In addition, DURECT will prepare annual safety reports covering all SUSARs that have occurred in clinical studies with the concerned test drug during the reporting period.

9.3.4 Adverse Event Follow-up

During and after participation by a patient in a clinical trial, the Investigator will ensure that adequate medical care has been provided to the patient for any AEs including clinically significant laboratory values related to the trial. The Investigator will inform the patient when medical care will be needed for intercurrent illness (es) of which Investigator becomes aware.

All SAEs and possibly/probably related severe AEs must be followed by the Investigator until resolution (no further changes in the event are expected, i.e., the point at which a patient experiencing such an AE has been appropriately treated and stabilized even though they may continue to experience lingering sequelae that may never resolve), until the patient is lost to follow-up, or died and until all queries related to the AEs have been resolved. If a patient dies during participation in the study or during a recognized follow-up period, the Sponsor (or designee) must be notified immediately and then provided with a copy of any post-mortem findings, including autopsy and histopathology.

9.4 **Pregnancy**

Serum pregnancy tests will be done at screening visit and Day 28 for females of child-bearing potential

Female patients will be advised to notify the Investigator immediately if they become pregnant during the course of the trial.

The Investigator must complete the appropriate pregnancy reporting forms and send them to DURECT (or DURECT's designee) within 14 calendar days of obtaining information of the pregnancy. The Investigator will follow the pregnancy through its course and complete the appropriate documentation and forward immediately to DURECT (or DURECT's designee). The infant must be followed at least until one month of age. Consent of a parent must be obtained before registration of infant data.

Abortion, stillbirth and any malformation/disease must be reported as an SAE. A pregnancy outcome other than abortion, stillbirth and any malformation/disease as well as follow-up of the infant must be reported by the Investigator within 14 calendar days of obtaining the information using the appropriate pregnancy reporting forms.

10.0 PHARMACOKINETICS

Plasma concentration data of DUR-928 from each patient will be used to calculate relevant pharmacokinetic parameters determined using standard non-compartmental method with linear/log-trapezoidal rule utilizing an appropriate pharmacokinetic data analysis program.

Pharmacokinetic parameters, such as C_{max} , T_{max} , $T_{1/2}$, AUC_{0-last} , AUC_{inf} , CL, and V_d , for DUR-928 will be calculated and summarized by dose group and Part A or B using descriptive statistics.

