5.0 CURRENT TRIAL

5.1 Trial Objectives and Primary Endpoints

- 1. Assess the safety and tolerability of DUR-928 in patients with AH as determined by the absence of SUSARs.
- 2. Determine the PK of DUR-928 in patients with AH.
- 3. Assess the pharmacodynamic signals of DUR-928 in patients with AH as determined by:
 - a. Biochemical: Improvement in liver biochemistry, MELD score, and the components of the MELD score individually (INR/sCr and bilirubin) at Day 7 and Day 28 and Lille score at Day 7
 - b. Biomarkers: improvement of biomarkers PPD/CCI

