5.2 Trial Rationale and Design

The study will be conducted in 2 Parts using a staggered parallel design. Part A will include patients with MELD scores of 11-20, and Part B will include patients with MELD of scores 21-30.

Within each Part, the study will be conducted using a starting dose level of 30 mg with sequential dose escalation following review of safety and PK results of the prior dose level by the sponsor, the principal investigators and the medical monitor. The planned subsequent doses of DUR-928 after the starting dose are 90 mg and 150 mg.

Patients with a MELD score of 21-30 (Part B) receiving the 30 mg dose level will only be enrolled once safety review of the 30 mg dose of DUR-928 in patients with MELD score 11-20 (Part A) has been completed. The subsequent dose escalation in each Part will not proceed until the sponsor, the principal investigators, and the medical monitor complete the review of safety and evaluate PK results of the 30 mg dose level and determine it is safe to do so.

If no SUSAR is observed and PK results are satisfactory, dose escalation to the next dose cohort will proceed. All patients will be followed up to Day 28.

Figure 1: Trial Schema

5.3 **Population**

[figure not shown]
Patients with AH will be enrolled at clinical sites in the US. The target number of participants to complete the study is 24-36. During the trial, patients should receive standard of care as determined by their PI.

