5.3.3 Number of Patients

Each dose cohort will have at least 4 and no more than 6 patients. There will be 3 dose cohorts in each part of the study. The total number of participants to complete the study is at least 24 and no more than 36.

5.3.4 **Dosage and Regimen**

by slow intravenous infusion over approximately 2 hrs PPD/CCI until entire dose is given. If a patient meets the hospital discharge criteria prior to the 2nd dose, the patient will receive only one dose of DUR-928 instead of 2 doses.

See Section 5.2 for details on dose escalation.

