11.5 General Statistical Analysis Considerations

The primary objective of this study is to assess dose-related safety and tolerability of DUR-928, with secondary objectives of assessing PK and dose-related evidence of potential efficacy of DUR-928. Study results for dose-related safety, efficacy, and PK profiles will utilize descriptive statistics.

Due to the small number of patients expected to be enrolled at each center, all summaries and analyses will be performed using data pooled across centers. Unless otherwise specified, continuous variables will be summarized by treatment cohort (DUR-928 dose levels) using the ITT analysis set with the number of non-missing observations, mean, standard deviation, median, 25th and 75th percentile, min, and max displayed. Categorical variables will be summarized by DUR-928 dose level using the ITT analysis set as counts and percentages. Missing data will not be estimated or carried forward in any of the analyses.

A thorough description of the statistical methods as well as presentation of study results will be developed and finalized prior to locking the database. Deviations from the statistical analysis plan (SAP) will be documented in the clinical trial report.

Except where other software maybe deemed more appropriate, all analyses will be performed using SAS Version 9.4 statistical software (SAS Institute, Cary, NC).

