14.4.1 Patient Withdrawal

Patients will be informed during the informed consent process (in writing and verbally) that they are free to withdraw from the trial at any time. The Investigator may exercise his medical judgment to terminate a patient's participation in the trial due to clinically relevant changes in any clinical or laboratory parameter.

DURECT

Corporation also reserves the right to terminate the trial at any time. All trial procedures normally performed at completion of the trial must be done at the time of the patient's early termination, before the scheduled final clinic visit, or on the scheduled final clinic visit as described in Section 7.2.7 unless the patient withdraws consent. If a patient withdraws consent they will be encouraged to complete an early termination visit and AE follow-up. Patients with ongoing SAEs and any possibly/probably related severe AEs will be followed until resolution. Resolution means no further changes in the event are expected, i.e., the point at which a patient experiencing such an AE is appropriately treated and stabilized even though they may continue to experience lingering sequelae that may never resolve. Patients with ongoing adverse events (other than SAEs, and any possibly/probably related severe AEs) will be followed until resolved or until 30 days after the patient's last trial visit, whichever comes first.

Patients who withdraw prior to assignment of test drug will be considered as screen failures. If a patient discontinues prior to completion of the 24 hour PK sample they will be replaced, since PK is one of the criteria for dose escalation assessment.

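### PK is only described in six dose-by-Part cells of 4 to 6 patients; an exploratory pooled log-scale fit with intervals would estimate the dose slope and the Part B/A ratio much more precisely by study end

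*Combined protocol and SAP*

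**What the plan says.** PK is the second listed objective in section 5.1: "Determine the PK of DUR-928 in patients with AH". Section 5.1 lists it among the objectives and primary endpoints, while section 11.5 calls it secondary. It also feeds the escalation decision. Section 5.2 states: "If no SUSAR is observed and PK results are satisfactory, dose escalation to the next dose cohort will proceed". Section 14.4.1 replaces patients who leave before the 24-hour sample, "since PK is one of the criteria for dose escalation assessment".

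On size, section 5.3.3 states: "Each dose cohort will have at least 4 and no more than 6 patients", then "There will be 3 dose cohorts in each part of the study", and "The total number of participants to complete the study is at least 24 and no more than 36".

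On analysis, section 10.0 derives Cmax, Tmax, half-life, two AUCs, clearance and volume by non-compartmental methods; these parameters "for DUR-928 will be calculated and summarized by dose group and Part A or B using descriptive statistics". Section 11.5 adds: "Study results for dose-related safety, efficacy, and PK profiles will utilize descriptive statistics". Unless otherwise specified, its statistics for continuous variables are n, mean, SD, median, quartiles, minimum and maximum. Confidence intervals are mentioned only in section 11.6, for demographic and baseline data. Sections 11.4 and 11.5 leave further detail to a SAP, and the available text contains no SAP section on PK.

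**The concern.** Dose (30, 90 and 150 mg) is crossed with MELD stratum (Part A 11-20, Part B 21-30). Every patient therefore carries information both on how exposure changes with dose and on whether exposure differs by severity. The planned tables use that information one cell at a time and attach no interval, so a reader comparing two cells cannot tell a real difference from chance. Exposure measures such as Cmax and AUC are positive and usually right-skewed. The natural comparisons are ratios, and geometric means support these better than arithmetic ones in cells this small.

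At stake is how firmly the study report can speak about the dose-exposure relation and about exposure in the sicker stratum. The data are already being collected, and the loss lies only in how they are summarised.

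**Working it through.** **Plan's own figure.** 2 Parts x 3 dose cohorts x 4 patients = 24, and x 6 patients = 36. This reproduces the range in section 5.3.3. Section 11.2 reports no formal sample size estimate, so there is no power or precision figure to reproduce.

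**Inputs.** Doses come from sections 5.2 and 7.1.1, and cell sizes from section 5.3.3. *Assumption:* the between-patient SD of log exposure is 0.5, with range 0.3 to 0.7, because the documents give none. All intervals are 90%. A factor F means that the limits are the estimate divided by F and multiplied by F.

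**Two single cells** (150 v 30 mg in one Part, or Part B v A at one dose): SE = SD x sqrt(2/n), with 2n-2 degrees of freedom.
- n=4: SE = 0.5 x sqrt(2/4) = 0.354; t(6) = 1.943; F = exp(0.687) = 1.99.
- n=6: SE = 0.5 x sqrt(2/6) = 0.289; t(10) = 1.812; F = exp(0.523) = 1.69.

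**Pooled fit**, ln(exposure) = a + b ln(dose) + c Part, with N-3 degrees of freedom.
- The log doses are 3.401, 4.500 and 5.011, with mean 4.304. The squared deviations are 0.815, 0.038 and 0.500, with mean 0.451.
- SE(b) = SD / sqrt(0.451 N). The 150 v 30 mg contrast is b x ln 5 = 1.609 b.
- N=24: SE(b) = 0.152; t(21) = 1.721; F = exp(1.721 x 0.152 x 1.609) = 1.52.
- N=36: SE(b) = 0.124; t(33) = 1.692; F = 1.40.
- SE(c) = 2 SD / sqrt(N). N=24: 0.204, so F = 1.42. N=36: 0.167, so F = 1.33.

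| Contrast, log-SD 0.5 | One pair of cells, n=4 / n=6 | Pooled fit, N=24 / N=36 |
|---|---|---|
| 150 v 30 mg | 1.99 / 1.69 | 1.52 / 1.40 |
| Part B v A | 1.99 / 1.69 | 1.42 / 1.33 |

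For log-SD 0.3 to 0.7 with N=24, the dose contrast runs from 1.51 to 2.62 by cell and from 1.29 to 1.80 by model.

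**Where the dose gain comes from.** Pool the Parts at 150 and at 30 mg, with no power model: SE = SD x sqrt(2/(2n)), with 4n-2 degrees of freedom. At n=4, SE = 0.25, t(14) = 1.761 and F = 1.55. At n=6, SE = 0.204, t(22) = 1.717 and F = 1.42. Most of the improvement is therefore the pooling of Parts. The power model takes it only from 1.55 to 1.52, or from 1.42 to 1.40.

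**When the gain arrives** (log-SD 0.5, n=4; the order of cohorts is illustrative).
- 1A alone: neither b nor c can be estimated.
- 1A and 2A: b is just the 30 v 90 mg cell contrast, and c cannot be estimated.
- 1A, 2A and 1B: three cell means and three parameters. The SE is 0.354 for both 90 v 30 mg and Part, the same as for the cells. F is 1.91 instead of 1.99, from degrees of freedom alone.
- Adding 2B: F = 1.56 for 90 v 30 mg and for Part.
- All cohorts except 3B: F = 1.51 for Part and 1.65 for 150 v 30 mg.

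**What the fit still cannot do.** The 90% half-width for b at log-SD 0.5 is 1.721 x 0.152 = 0.262 (N=24) or 0.210 (N=36). Suppose proportionality meant a dose-normalised ratio within 0.8 to 1.25 over the five-fold range, a criterion that is not in the documents. The interval would then have to lie within 1 +/- ln(1.25)/ln(5) = 1 +/- 0.139. At log-SD 0.3 the half-width is 0.157 (N=24) or 0.126 (N=36), so only the larger trial with low variability could meet it. A difference in slope between Parts has twice the SE of b. Its half-width at log-SD 0.5 is about 0.52 (N=24) or 0.42 (N=36).

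**The case against.** A descriptive PK summary is a legitimate choice for an open-label Phase 2a study of 24 to 36 patients with no formal sample size. Several specific points stand:

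- Neither dose proportionality nor a severity effect on exposure is a stated objective or escalation criterion. The design raises both questions, but the documents do not pose them.
- Clearance for an intravenous drug is dose divided by AUC to infinity, so clearance by dose and Part already displays dose-normalised AUC. Only dose-normalised Cmax would be new, and what is missing is the pooled estimate and its interval.
- Section 11.5 lists median, quartiles and range, which suit skewed data. Its list is a default, and the term descriptive statistics in section 10.0 does not exclude geometric means.
- The SAP may add methods, so the gap is shown only for the text available.

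A reader might also infer that the escalation decisions rest on inadequate PK analysis and that this model would repair them. The documents and the arithmetic do not support that. The model is inestimable or saturated through the first three cohorts, and its full gain exists only once no escalation decision remains. Nor would it be right to call the cell summaries too imprecise to use. No precision target is stated, and at log-SD 0.3 with n=6 the cell factor is only 1.37.

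**Conclusion.** The point holds as a cheap improvement to the end-of-study PK analysis. By cell, the 150 v 30 mg and Part B/A comparisons carry 90% factors of 1.99 (n=4) or 1.69 (n=6). Pooling brings them to 1.52 or 1.40 for dose and to 1.42 or 1.33 for Part, with no extra patients or samples. These sizes rest on an assumed log-SD of 0.5, one variance for all cells, one slope in both Parts, and every enrolled patient being PK-evaluable. The direction of the gain holds over log-SD 0.3 to 0.7.

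It would be tempting to say that one model settles both dose proportionality and the effect of liver severity. It does not. It estimates both with intervals, and those intervals would seldom satisfy a tight proportionality criterion.

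**What to change.** In section 10.0 (or the SAP's PK section):

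1. Keep the dose-by-Part tables. Add geometric mean and geometric CV% for Cmax, AUC and clearance, and add dose-normalised Cmax.
2. Pre-specify an exploratory regression of first-infusion ln(Cmax) and ln(AUC) on ln(dose) and Part. Using the first infusion keeps patients who are discharged before the second dose. Report the slope and the Part B/A ratio with 90% confidence intervals.
3. Add a dose-by-Part term as a check on the common slope, noting that it will be poorly estimated.
4. State that the analysis estimates, and does not establish, dose proportionality and the severity effect, and that it is intended mainly for the end of the study.

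The cost is a few lines of text and one regression per parameter on data already collected. The small downside is reliance on a common slope and variance across Parts. Nothing changes in dosing, sampling, sample size or the escalation process.
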